8.4 Withdrawal of individual subjects

Subjects can leave the trial at any time for any reason if they wish to do so without any consequences. The sponsor can decide to withdraw a subject from the trial for urgent medical reasons.

8.5 Replacement of individual subjects after withdrawal

Subjects will not be replaced after withdrawal from the trial unless a subject withdraw his or her consent before the start of procedure.

8.6 Premature termination of the study

A possible reason to prematurely end the study could be based on a decision of the sponsor. In that case a written statement will be prepared for the Medical Ethics Committee (MEC).

9. SAFETY REPORTING

9.1 Temporary halt for reasons of subject safety

In accordance to section 10, subsection 4, of the Medical Research involving Human Subjects Act (WMO), the sponsor will suspend the trial if there is sufficient ground that continuation of the trial will jeopardise subject health or safety. The sponsor will notify the accredited MEC without undue delay of a temporary halt including the reason for such an action. The trial will be suspended pending a further positive decision by the accredited MEC. The investigator will take care that all subjects are kept informed.

9.2 AEs and SAEs

9.2.1 Adverse events (AEs)

Adverse events (AEs) are defined as any undesirable experience occurring to a subject during the trial, whether or not considered related to coronary procedures. All AEs reported spontaneously by the subject or observed by the investigator or his staff will be recorded starting from enrolment onwards until follow-up or the staged procedure in a subset at 4 ± 2 weeks. Unchanged chronic conditions are not AEs and should not be recorded on the AE sheet.

9.2.2 Serious adverse events (SAEs)

A serious adverse event (SAE) is any untoward medical occurrence or effect that

- results in death;
- is life threatening (at the time of the event);
- requires hospitalization or prolongation of existing inpatients' hospitalization*;
- results in persistent or significant disability or incapacity;
- is a congenital anomaly or birth defect; or
- any other important medical event that did not result in any of the outcomes listed above due to medical or surgical intervention but could have been based upon appropriate judgement by the investigator.

***Hospitalization:**

Any AE leading to hospitalization or prolongation of hospitalization will be considered as serious, unless the admission is:

- planned before subject's inclusion in the trial (i.e. elective or scheduled surgery) or
- ambulant (shorter than 12 hours) or
- part of the normal treatment or monitoring of the studied disease (i.e. not due to a worsening of the disease)

9.3 Follow-up of adverse events

All AEs will be followed until they have abated, or until a stable situation has been reached. Depending on the event, follow up may require additional tests or medical procedures as indicated, and/or referral to the general physician or a medical specialist. AEs will not be followed up on once patients finish the study after 4 weeks.

SAEs will be collected and monitored throughout the entire course of the trial.

9.4 Adverse event reporting

Each AE or complication meeting the definition for SAE will be reported by site upon discovery to the Clinical Research Organization (CRO)/sponsor, within 24 hours of the site investigator's knowledge of the event. The accredited MEC will receive an overview of all SAEs annually.

10. STATISTICAL ANALYSIS

The principal features of the statistical analysis of the data are described in this chapter. A more technical and detailed elaboration will be written in a separate statistical analysis plan (SAP).

10.1 General methods

In general, statistics for continuous variables will include mean, median, standard deviation, minimum, maximum, 25th and 75th percentile. Binary variables will be described with frequencies, percentages.

10.2 Analysis primary outcome

Primary objective of the study is to evaluate non-inferiority of with a pre-specified non-inferiority margin of 0.10 and AUC of 0.90. The hypothesis for testing non-inferiority is

$$H_0: AUC_{RFR} - AUC_{FFR} \leq -0.10$$

$$H_1: AUC_{RFR} - AUC_{FFR} > -0.10$$

Non-inferiority is established if the lower limit of a $(1-2\alpha) \times 100\%$ confidence interval of the difference between AUC_{RFR} and AUC_{FFR} is above -0.10 rather than the usual $(1 - \alpha) \times 100\%$ confidence interval. We will construct a 90% 2-sided confidence interval and use the lower bound to determine non-inferiority. If the lower boundary of the 90%CI of the difference is above -0.10 than RFR is non-inferior to FFR. If the lower boundary of the 90%CI of the difference is below -0.10 than RFR is inconclusive or inferior to FFR.

10.3 Analysis of secondary outcomes

Pearson r correlation and Spearman correlation coefficient rho (r) will be used to evaluate the degree of relationship between variables. For normally distributed variables, we will use the Pearson r correlation, while in case of skewed, ordinal data, the degree of association between variables will be quantified using Spearman correlation coefficient rho (r).

For repeated measurements (RFR, FFR, and other physiological parameters) we will use the paired t test for normally distributed variables and the Wilcoxon signed-rank test for skewed continuous data.

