8.1.2 Secondary study endpoints (definitions in appendix I)

Secondary endpoints are defined as :

- The predictive value of the RFR and FFR gradient across the stented segment with regard to SSR in CTO patients.
- The correlation between positive RFR (≤ 0.89) and positive FFR (≤ 0.80) with regard to SSR following angiographically satisfactory CTO PCI.
- The correlation between post-PCI physiology (RFR, FFR, CFR, IMR) and SSR with anginal complaints (SAQ score), NYHA and CCS classification and MACE at follow-up.

- The correlation between OCT and/or physiology findings and physician-decision making (perform or refrain from additional PCI)

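### Section 10.3 names only correlation for the secondary endpoints, although one asks for predictive value and the rest involve yes/no variables; a coefficient does not report predictive value

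*Protocol*

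**What the plan says.** Protocol section 10.3, the section on secondary outcomes, says that "Pearson r correlation and Spearman correlation coefficient rho (r) will be used to evaluate the degree of relationship between variables". Pearson is for normally distributed variables; "while in case of skewed, ordinal data, the degree of association between variables will be quantified using Spearman correlation coefficient rho (r"). Binary variables are not mentioned. The only other methods there are for repeated measurements: "we will use the paired t test for normally distributed variables and the Wilcoxon signed-rank test for skewed continuous data". AUC is specified only for the primary outcome, in 10.2.

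Section 8.1.2 lists four secondary endpoints:

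1. "The predictive value of the RFR and FFR gradient across the stented segment with regard to SSR in CTO patients".
2. "The correlation between positive RFR (≤ 0.89) and positive FFR (≤ 0.80) with regard to SSR following angiographically satisfactory CTO PCI".
3. Post-PCI physiology and SSR "with anginal complaints (SAQ score), NYHA and CCS classification and MACE at follow-up".
4. "The correlation between OCT and/or physiology findings and physician-decision making (perform or refrain from additional PCI").

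The opening of section 10 says that it holds the main features of the analysis and that a separate SAP will elaborate. That SAP is not at hand.

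**The concern.** The method named in 10.3 and the endpoints listed in 8.1.2 do not match well. Endpoint 1 is a question of discrimination. The primary objective uses the same phrase, predictive value, and 10.2 answers it with AUC, but 10.3 offers only a correlation. Endpoint 2 relates three yes/no variables, which a single two-variable coefficient does not describe. MACE in endpoint 3 and the operator's decision in endpoint 4 are also yes/no. The selection rule (normal, or skewed and ordinal) fits none of these binary variables.

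What is at stake is reporting and interpretation. A reader who wants to know how often a low RFR signals a suboptimal stent would receive a number that does not say so. A small coefficient for a rare event could also be taken for a weak relationship when the event rate itself limits it.

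**Working it through.** The protocol gives no figure for the secondary analyses, so there is none to reproduce. The check is first a comparison of endpoint type with named method, then a calculation of what a coefficient conveys.

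**Endpoint type against the rule in 10.3**

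| Endpoint (8.1.2) | Variables | Covered by the rule? |
|---|---|---|
| 1 Gradients and SSR | continuous, binary | Not for predictive value; SSR is binary |
| 2 RFR ≤0.89, FFR ≤0.80, SSR | three binary | No |
| 3 Physiology and SSR with SAQ, NYHA, CCS, MACE | mixed | Spearman suits SAQ, NYHA and CCS; MACE and SSR are binary |
| 4 Findings and decision | decision is binary | No |

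**Inputs**

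- SSR prevalence 40% and AUC 0.90 for FFR: protocol 6.4 (planning assumptions).
- One-third of patients with FFR ≤0.80: protocol section 3, from a cited series of 26 patients.
- MACE rate: not given. Assumed range 2%, 5%, 10%.

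**Step 1: one coefficient, different predictive values.** On two binary variables Pearson and Spearman both equal phi. With prevalence p, sensitivity Se, specificity Sp and proportion test-positive q = Se·p + (1−Sp)(1−p):

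phi = (Se·p − q·p) / √[p(1−p)q(1−q)]

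- Se 0.90, Sp 0.60, p 0.40: q = 0.36 + 0.24 = 0.60; phi = (0.36 − 0.24)/√(0.24 × 0.24) = 0.50. PPV = 0.36/0.60 = 0.60; NPV = 0.36/0.40 = 0.90.
- Se 0.50, Sp 0.935, p 0.40: q = 0.20 + 0.039 = 0.239; phi = (0.20 − 0.0956)/√(0.24 × 0.239 × 0.761) = 0.50. PPV = 0.20/0.239 = 0.84; NPV = 0.561/0.761 = 0.74.

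These two tests would be used quite differently, yet they share one coefficient.

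**Step 2: ceiling on phi.** For prevalences p < q the maximum is √[p(1−q)/(q(1−p))]. Against 40% SSR:

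- FFR ≤0.80 in one-third: √(0.200/0.267) = 0.87.
- MACE 2%: √(0.012/0.392) = 0.175.
- MACE 5%: √(0.03/0.38) = 0.28.
- MACE 10%: √(0.06/0.36) = 0.41.

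The MACE ceilings hold even if every event falls in a patient with SSR.

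**Step 3: continuous index, binary outcome.** With no ties in the index, Spearman rho = (2·AUC − 1)·√[3p(1−p)]. For AUC 0.90:

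- p = 0.40: 0.8 × √0.72 = 0.68.
- p = 0.10: 0.8 × √0.27 = 0.42.
- p = 0.05: 0.8 × √0.1425 = 0.30.
- p = 0.02: 0.8 × √0.0588 = 0.19.

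The same discrimination therefore gives coefficients from 0.68 down to 0.19, depending only on how common the outcome is.

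**The case against.** The strongest reply has five parts.

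- **The binary cases may be unspecified rather than wrongly specified.** The rule in 10.3 never mentions yes/no variables, and section 10 defers detail to a SAP. This stands in part: a missing method for the gradients, taken alone, could be left to the SAP. But 10.3 states its method for relationships without restriction. A SAP that used AUC or sensitivity and specificity would be replacing that method, not elaborating it.
- **Three of the four endpoints are worded as correlations, and a coefficient answers a question about correlation.** This stands. Phi and point-biserial coefficients validly measure and test association; in a 2×2 table chi-square equals n times phi squared, so the ceiling does not invalidate the test. Spearman is suitable for SAQ, CCS and NYHA.
- **Predictive value already means AUC in this protocol.** That is the natural reading of endpoint 1, and nothing in 10.3 forbids it. It is also the reason to write it down.
- **Prevalence matters little within one cohort.** This stands for comparing RFR with FFR against SSR, where prevalence is common to both. It does not help when coefficients for SSR and for MACE are read side by side.
- **The MACE rates are assumed.** This stands. At 2% to 5% of 200 patients there would be 4 to 10 events, and no method would extract much from them.

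A reader might go further and infer that correlation cannot answer these endpoints, or that the trial could not report predictive value at all. The documents do not support that. The coefficients are valid tests; with prevalence known and no ties, AUC can be recovered from rho; and 10.1 commits to frequencies for binary variables. Nor is a paired test of the two cut-offs missing: endpoint 2 does not ask for one, and the paired RFR-versus-FFR comparison is the primary analysis.

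**Conclusion.** The point holds as a minor mismatch between stated method and stated endpoints. Section 10.3 names only Pearson or Spearman correlation, while 8.1.2 contains a predictive-value endpoint and several yes/no variables that its selection rule does not fit. The coefficient is valid as a test of association, but it does not report predictive value and its size moves with prevalence.

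The firmest illustration is Step 1, which needs only the protocol's assumed 40% SSR: phi of 0.50 is compatible with a PPV of 0.60 or 0.84. The sensitivity/specificity pairs are illustrative, not forecasts. The ceiling built on the protocol's own figures, 0.87, is mild; the low ceilings of 0.175 to 0.41 rest on assumed MACE rates. The primary non-inferiority analysis, the sample size of 190 (200 with dropout) and the data to be collected are untouched.

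**What to change.** Reword 10.3 so that the method follows the type of endpoint, replacing correlation where it does not fit:

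- RFR and FFR gradients against SSR: AUC with confidence interval, matching the primary analysis.
- RFR ≤0.89 and FFR ≤0.80 against SSR: sensitivity, specificity, PPV and NPV, each with a confidence interval.
- MACE and the operator's decision: a method for binary outcomes, such as risk differences or odds ratios with confidence intervals.
- SAQ, CCS and NYHA: keep Spearman.

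The SAP should carry the same wording. McNemar tests within SSR groups or penalised logistic regression are options, not requirements. The cost is a few sentences, settled before the data are analysed; no extra patients, measurements or follow-up are needed.

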10.4 Safety analysis

The number, nature, frequency, severity and treatments will be described.

11. ETHICAL CONSIDERATIONS

11.1 Regulation statement

The trial will be conducted in compliance with the protocol, principles of the Declaration of Helsinki (2013), WMO, ICH-Good Clinical Practice, as well as local regulations and applicable regulatory requirements.

11.2 Recruitment and consent

Eligible patients meeting the inclusion criteria will be asked for IC by one of the cardiologists. Written IC will be obtained before the index PCI procedure. The information is intended to give each participant a thorough understanding of the purpose and the nature of the trial, the cooperation required, anticipated benefits, and potential hazards of the trial. The cardiologist also explains that the patient is completely free to refuse or to withdraw from the trial and that if he does so he receives standard treatment with the same degree of care.

11.3 Benefits and risks assessment and group relatedness

The anticipated benefit is improvement of our knowledge on how to optimize stent results in CTO PCI.

Because the pressure wires and OCT camera that are used for the study-related measurements are commonly used interventional tools, this poses no study-related additional risk for participating patients. International guidelines recommend the use of intravascular imaging for PCI guidance, especially in complex cases leading to lower myocardial infarction, TVR and cardiac mortality. Pressure wires are clinically indicated to identify hemodynamic significant (remaining) lesions that needs to be revascularized. Due to study-related measurements the procedures will be moderately prolonged, most likely by approximately 15 minutes. With minimal effort and risk, subjects included in this trial are able to contribute to research to that may improve the treatment of CTOs, which may have large impact on clinical practice and guidelines.

11.4 Compensation for injury

The investigator has a liability insurance which is in accordance with article 7 of the WMO. The sponsor will arrange an insurance which is in accordance with the legal requirements in the Netherlands (Article 7 WMO). This insurance provides cover for damage to research subjects through injury or death caused by the trial.

12. ADMINISTRATIVE ASPECTS, MONITORING AND PUBLICATION

12.1 Handling and storage of data and documents

Electronic Case Report Forms (eCRFs) have been developed to capture the trial information outlined in this protocol. Data from these eCRFs will be used in the analysis of trial results. Modification of the eCRFs will only be made if deemed necessary by the sponsor.

Data entered in to the eCRFs will be taken from source documentation, such as hospital procedure reports, admission and discharge summaries and other hospital or physician office/clinic documents. If no standard hospital or office document exists to capture some of the information that may be unique to this trial, a worksheet may be developed to record this information and be used as a source document. This worksheet needs to be signed by the person responsible for the registered data on the worksheet at the given site. These source documents will serve as the basis for monitoring the eCRFs. Electronic patient records will be considered as source documents on the condition that the hospital's database is a validated system. If this is not the case, electronic records will have to be printed and added to the paper patient file. A print-out of the eCRF cannot be used as source documentation.

The investigator will maintain all records pertaining to this trial for fifteen years following trial completion, or as otherwise instructed by the CRO, or per local requirements whichever is longer. Published data will not be traceable to the individual patient.

12.2 Monitoring and Quality Assurance

CRO and/or designee will monitor the trial over its duration according to the pre-specified monitoring plan. This will be done by means of personal visits to the site's facilities, telephone contacts to the investigator or designee, and/or remotely through the internet-based database with verification of the source data. The trial monitor may inspect all documents and required documents that are maintained by the investigator/site, including medical records (office, clinic or hospital) for the subjects in this trial. The investigator/site will permit access to such records.

Source documentation must be available to substantiate proper IC procedures, adherence to protocol procedures, adequate reporting and follow-up of adverse event and accuracy of data collected on case report forms. A monitoring visit log will be maintained at the site. The investigator and/or research coordinator will be available for monitoring visits. It is expected that the investigator will provide the trial monitor with a suitable working environment for review of trial-related document.

A comprehensive, integrated data management plan, including on-line queries and (remote) data cleaning will be implemented to ensure the integrity of the data. All changes to the database will be tracked by an audit trail.

All site personnel will be trained on the protocol and internet-based database prior to the initiation of the trial at each respective site. Only trained (site) personnel will receive access to the internet-based database by means of a personalized username and password.

12.3 Amendments

Amendments are changes made to the research after a favourable opinion by the accredited MEC has been given. All amendments will be notified to the MEC that gave a favorable opinion.

12.4 Annual progress report

A summary of the progress of the trial will be submitted to the accredited MEC once a year. Information will be provided on the date of inclusion of the first subject, numbers of subjects included and numbers of subjects that have completed the trial, serious adverse events, other problems, and amendments.

12.5 Temporary halt and (prematurely) end of study report

The sponsor will notify the accredited MEC of the end of the trial within a period of 8 weeks. The end of the trial is defined as the last patient's last visit.

The sponsor will notify the MEC immediately of a temporary halt of the trial, including the reason of such an action.

In case the trial is ended prematurely, the sponsor will notify the accredited MEC within 15 days, including the reasons for the premature termination.

Within one year after the end of the trial, the sponsor will submit a final trial report with the results of the trial, including any publications/abstracts of the trial, to the accredited MEC.

12.6 Publication policy

This trial will be registered at www.clinicaltrials.gov. The results of this prospective, multicentre, non-randomised investigator-initiated trial with a non-inferiority design are intended to be published in a peer-reviewed journal and as abstracts/presentations at medical congresses. The publication rights in regard to the main results of the trial, i.e., regarding the primary and secondary objectives, belong to the sponsor. No individual investigator may publish on the results of this trial, or their own patients, without prior approval from the sponsor. A minimum number of subjects per site needs to be included in the trial by the investigator in order to be considered as co-author for publication. This is further defined in a separate clinical trial agreement with each participating site.

14. APPENDIX I: RELEVANT DEFINITIONS

Angiographic success	Successful PCI of the target lesion with a residual stenosis of less than 30% angiographically.
CCS	Canadian Cardiovascular Society.
Clinical classification	CCS classification, NYHA classification and at staged procedure also SAQ score, TLR, ST, MACE, TVF.
CTO	Lesion exhibiting TIMI 0-1 flow in a native coronary artery with an occlusion duration > 3 months ¹⁴ .
Geographical miss	Incomplete stent coverage of plaques within 10 mm distal or proximal to the stent edges with residual stenosis on OCT of \geq 50% cross-sectional area (CSA) as compared to the reference lumen area.
Intrastent plaque-protrusion	Distance between strut surface and the greatest extent of protrusion $>100 \mu\text{m}$ ¹⁵ .
Intrastent thrombus-protrusion	Irregular mass protruding into lumen $>250 \mu\text{m}$ at the thickest point; thrombus may not be connected to the vessel wall ¹⁵ .
MACE	Composite endpoint of all-cause mortality, myocardial infarction and any coronary revascularization.
Microvascular dysfunction	IMR > 25 .
Myocardial infarction	Defined according to the expert consensus document ¹⁶ .
NYHA	New York Heart Association.
Pd/Pa	Pressure-distal / pressure-aorta = ratio of mean resting distal coronary pressure to aortic pressure
Reference lumen area	The average of the two largest lumen areas proximal and distal to a stenosis but within the same segment (usually within 10 mm) ¹⁷ .

Repeat revascularization	PCI or CABG (with specification of target vessel revascularization).
SAQ	Seattle Angina Questionnaire ¹² .
Sponsor	The sponsor is the party that commissions the organisation or performance of the research, for example a pharmaceutical company, academic hospital, scientific organisation or investigator. A party that provides funding for a study but does not commission it is not regarded as the sponsor, but referred to as a subsidising party.
Stent edge dissection (clinically relevant)	Dissection width $\geq 200 \mu\text{m}$, and/or dissection angle $\geq 60^\circ$, and/or dissection length $> 0.67 \text{ mm}$ ¹⁵ . Stent edge dissections meeting these criteria are considered components of SSR.
Stent edge dissection (other)	Stent edge dissections not meeting the criteria of clinically relevant stent edge dissections.
Stent malapposition	Distance from the center of the stent blooming artifact to the vessel wall of $\geq 200 \mu\text{m}$ ¹⁵ and present in at least 5 consecutive OCT frames ⁶ .
Stent thrombosis	Presence of a thrombus that originates in the stent or in the segment 5 mm proximal or distal to the stent ¹⁸ .
Stent underexpansion	In-stent minimal lumen area less than 90% of the average reference lumen area ¹⁵ .
TLR	Re-intervention of the treated segment within 5 mm proximal or distal to the stent ¹⁸ .
TVF	Composite endpoint of cardiac death, target-vessel myocardial infarction and clinically driven target-vessel revascularization.
